8.4.1 Missing Data Conventions

Missing values of safety parameters will not be imputed.

The weekly BM (SBM, CSBM) rate is the sum of the BMs (SBMs, CSBMs) recorded for the days in the week for which a BM response is recorded in the daily diary. Note that this is equivalent to a “worst case” analysis in that the BM (SBM, CSBM) rate for the week is the sum of the BMs (SBMs, CSBMs) recorded for the days in the week for which BMs were reported, plus 0 BMs (SBMs, CSBMs) for each day in the week for which the BM response is missing. In any week in which no BM response is recorded, the weekly BM (SBM, CSBM) rate will be set to 0 in any summary or linear mixed-effects model analysis involving

the weekly BM (SBM, CSBM) rate. In particular, for a randomized patient who withdraws from study participation prior to the end of the study, the patient is considered to have a weekly BM (SBM, CSBM) rate equal to 0 for any weeks remaining in the planned duration of the study for which the patient has no BM responses recorded.

The weekly average IBS-related daily abdominal pain score is the average of the non-missing, abdominal pain scores recorded in that week, i.e., the weekly average is the sum of the abdominal pain scores recorded in the diary in the given week, divided by the number of pain scores recorded in the week. In any week in which a patient has no diary days for which an abdominal pain score is recorded, the weekly average abdominal pain score will be set to missing. In any linear mixed-effects model analysis involving the weekly average abdominal pain score, if the average score is set to missing in a given week, it will be left as missing in the linear model. In particular, for a randomized patient who withdraws from study participation prior to the end of the study, the weekly average abdominal pain score will be set to missing for any weeks remaining in the planned duration of the study for which the patient has no abdominal pain data.

In any analysis of the frequency of fecal incontinence, the frequency of defecation pain, and the frequency of large diameter stools will follow the same methodology as described above for the determination and analysis of the weekly BM rate.

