3.3.4. Missing Data

Missing values of safety parameters will not be imputed.

For each day in the week for which the Bowel Movement (BM) (includes Spontaneous Bowel Movement [SBM] and Complete Spontaneous Bowel Movement [CSBM]) response is missing, 0 BMs (SBMs, CSBMs) will be used, and any week in which no BM response is recorded, the weekly BM (SBM, CSBM) rate will be set to 0. In particular, for a randomized subject who withdraws from study participation prior to the end of the study, the subject is considered to have a weekly BM (SBM, CSBM) rate equal to 0 for any weeks remaining in the planned duration of the study for which the subject has no BM responses recorded.

In any analysis of the frequency of abdominal pain (discomfort), use of rescue medication, the frequency of fecal incontinence, the frequency of defecation pain, the frequency of large diameter stools, missing values will be imputed to zero.

In any analysis involving the severity of abdominal pain and discomfort, the weekly average IBS-related daily abdominal pain (discomfort) score is the average of the non-missing, abdominal pain (discomfort) scores recorded in that week, i.e., the weekly average is the sum of the abdominal pain (discomfort)

scores recorded in the diary in the given week, divided by the number of pain (discomfort) scores recorded in the week. In any week in which a subject has no diary days for which an abdominal pain (discomfort) score is recorded, the weekly average abdominal pain (discomfort) score will be set to missing. In particular, for a randomized subject who withdraws from study participation prior to the end of the study, the weekly average abdominal pain (discomfort) score will be set to missing for any weeks remaining in the planned duration of the study for which the subject has no abdominal pain (discomfort) data.

In any analysis involving the severity of defecation pain, the weekly averages are the sum of the non-missing severity of defecation pain scores recorded during the week, divided by the total number of non-missing severity of defecation pain scores recorded. In any week in which a subject has no non-missing severity of defecation pain scores recorded, the weekly average score will be set to missing in any summary or linear mixed-effects model analysis involving the weekly average severity of defecation pain score.

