A Treatment-emergent Laboratory Toxicity is defined as any post-baseline laboratory assessment occurring up to and including 14 days post treatment discontinuation representing an increase of 1 grade or more from the baseline toxicity value. If the baseline value is missing, any graded toxicity (grade 1 or higher) that occurs following initiation of treatment is considered treatment-emergent.

Spontaneous bowel movement (SBM)

A bowel movement that occurs in the absence of laxative use within the preceding 24 hours.

Complete spontaneous bowel movement (CSBM)

A spontaneous bowel movement with the sense of complete evacuation.

Weekly BM (SBM, CSBM) Rate

Weekly BM (SBM, CSBM) rate is the sum of the BMs (SBMs, CSBMs) recorded for the days in the week for which a BM (SBM, CSBM) response is recorded in the daily diary.

In any analysis of the frequency of abdominal pain, frequency of abdominal discomfort, frequency of fecal incontinence, the frequency of defecation pain, and the frequency of large diameter stools will follow the same methodology as described above for the determination and analysis of the weekly BM rate.

Weekly Average Abdominal Pain Score

Weekly average IBS-related daily abdominal pain score is the average of the non-missing, abdominal pain scores recorded in that week, i.e., the weekly average is the sum of the abdominal pain scores recorded in the diary in the given week, divided by the number of pain scores recorded in the week.

Weekly Average Defecation Pain Score

Weekly average item score is the sum of the non-missing defecation pain scores recorded during the week, divided by the total number of non-missing defecation pain scores recorded.

Weekly Average Stool Consistency

Stool consistency is the sum of the non-missing stool consistency scores recorded during the week, divided by the total number of non-missing stool consistency scores recorded. Note stool consistency cannot be assessed if the subject does not have at least one SBM during the week in question (i.e., stool consistency is based on SBMs only).

Concomitant Medications

Concomitant medications are those medications taken on or after the initiation of study drug. This definition includes medications started prior to the initiation of study drug but continuing concomitantly with study drug.

Prior Medications

Prior medications are those medications taken and ended prior to the initiation of study drug.

Post Medications

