4.2. PER PROTOCOL (PP) POPULATION

All subjects in the FAS population who complete the 4-week Treatment Period or discontinue from study treatment due to adverse event(s) or lack of efficacy, with the exception of major protocol violators. If a diary compliance is < 70% or treatment compliance is < 80% then the subject is excluded from the PP Population. Subjects with Week 4 visit outside of the window 28 +/- 3 (study days 25 to 31) days will be excluded from the PP Population. Final decisions regarding exclusion from the PP Population will be made prior to unblinding the database.

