The weekly average abdominal pain and abdominal discomfort scores will be determined using the approach defined in [Section 3.3.7](#) with missing scores excluded as described in [Section 3.3.4](#) and presented for each week in the 4-week treatment period. The change from baseline in the weekly averaged abdominal pain and abdominal discomfort scores will be analyzed in the FAS Population using a linear mixed-effects ANCOVA model with fixed effects for gender (stratification variable), treatment, week, the interaction of treatment and week, and the corresponding baseline value; a random intercept for subject will also be specified. The least squares (LS) means, with 95% confidence intervals and the corresponding statistical p-value, will be presented for each week, and across all 4 weeks, of the 4-week treatment period for the difference between the difference in LS means for each of treatment group versus placebo, combined active doses within each age group versus placebo, and overall active doses versus placebo. The analysis of interest for this secondary endpoint is the difference in LS means between each plecanatide group (each dose within each age group, combined active dose within each age group, and overall active dose) versus placebo for the estimated overall average change from baseline in abdominal pain and abdominal discomfort scores across the 4-week treatment period.

Baseline abdominal pain and abdominal discomfort will be calculated as the equally weighted average of the average abdominal pain (or abdominal discomfort) for each of the two weeks prior to initiation of study drug.

The above analysis will be repeated for the PP Population.

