5.2.4.5. Use of Rescue Medication

The proportion of subjects who used at least one dose of rescue medication during the treatment period, will be summarized by treatment group. The number of tablets of rescue medication used per week, and overall, for the 4-week treatment period will be analyzed by treatment group. The Mann Whitney U Test (Wilcoxon Rank Sum Test) will be used to compare the difference between each treatment group, combined active doses within each age group, and overall active doses, versus Placebo at each week, and over all 4 weeks, of the 4-week treatment period.

The above analysis will be repeated for the PP Population.

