5.2.4.7. Change from Baseline in Frequency and Severity of Defecation Pain

The weekly defecation pain rate for each subject will be computed, as described in [Section 3.3.7](#), for each week of the 4-week treatment period and for the two weeks of the follow-up period. A summary, by treatment group, of the mean weekly defecation pain rate, and change from baseline in mean weekly defecation pain rate, for each of the 6 study weeks will be presented. The change from baseline in mean weekly defecation pain rate will be analyzed using a linear mixed-effects model with fixed effects for gender (stratification variable), treatment, week, the interaction of treatment and week, and the corresponding baseline value; a random intercept for subject will also be specified. The least squares (LS) mean change from baseline will be presented, by treatment groups, and the difference in LS means for each treatment group versus placebo and combined active doses within each age group versus placebo in a separate model for each age group, and overall active doses versus placebo in a separate model with 95% confidence intervals and corresponding statistical p-values.

The weekly average defecation pain score will be determined using the approach defined in [Section 3.3.7](#) and presented for each week in the 4-week treatment period. The change from baseline in the weekly averaged defecation pain score will be analyzed in the FAS Population using a linear mixed-effects model with fixed effects for gender (stratification variable), treatment, week, the interaction of treatment and week, and the corresponding baseline value; a random intercept for subject will also be specified. The least squares (LS) means, with 95% confidence intervals and the corresponding statistical p-value, will be presented for each week, and across all 4 weeks, of the 4-week treatment period for the difference between the difference in LS means for each of treatment group versus placebo, combined active doses within each age group versus placebo, and overall active doses versus placebo. The analysis of interest for this secondary endpoint is the difference in LS means between each plecanatide group (each dose within each age group, combined active dose within each age group, and overall active dose) versus placebo for the estimated overall average change from baseline in defecation pain and defecation pain scores across the 4-week treatment period.

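### SAP 3.3.4 replaces missing symptom frequencies and rescue use with zero, the most favourable value, so unrecorded days and weeks count as event-free

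*Combined protocol and SAP*

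**What the plan says.** SAP 3.3.4 covers the frequency of abdominal pain, abdominal discomfort and fecal incontinence, rescue use, "the frequency of defecation pain, the frequency of large diameter stools, missing values will be imputed to zero". SAP 3.3.7 then ties the symptom frequencies, but not rescue use, to the bowel movement (BM) derivation: "frequency of abdominal discomfort, frequency of fecal incontinence, the frequency of defecation pain, and the frequency of large diameter stools will follow" the method used for the weekly BM rate. Under that method each missing day adds 0, and each week after withdrawal without BM data is scored 0. For rescue use, a zero after withdrawal rests only on the general sentence in SAP 3.3.4.

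Protocol 8.4.1 gives the reason for zero-filling: "Note that this is equivalent to a “worst case” analysis in that the BM" count for a day without a response is taken as 0. It applies the BM method to fecal incontinence, defecation pain and large diameter stools. It states no frequency rule for abdominal pain or discomfort, although protocol 8.8.2.1 refers to it for those rates, and no rule for rescue use. The explicit zero for those outcomes appears in the SAP and is not listed among the changes in SAP section 7.

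Severity is handled differently. After withdrawal, "the weekly average abdominal pain (discomfort) score will be set to missing for any weeks remaining in the planned duration of the study" (SAP 3.3.4). Rescue tablets are compared by rank test: "The Mann Whitney U Test (Wilcoxon Rank Sum Test) will be used to compare the difference between each treatment group" and placebo (SAP 5.2.4.5).

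**The concern.** A rule that is unfavourable for one kind of outcome has been carried over to outcomes where it is favourable. A missed day lowers a BM count, which is a worse result. The same missed day lowers a count of pain days, incontinence episodes, large stools or rescue tablets, which is a better result. A child who leaves after Week 1 is recorded with no pain days in Weeks 2 to 4, while the pain severity for those weeks is missing.

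Two errors follow. Change from baseline is overstated in any arm with more missing data on treatment than at baseline. Between arms, the group with more missing data looks better, so unequal withdrawal can create a false benefit or hide a real one. For fecal incontinence, large stools and rescue use, no other planned analysis in the full analysis set would show it.

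**Working it through.** The plan states no figure on this point. Its only power calculation concerns SBM frequency and is not used here.

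**The rules side by side**

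| Outcome | Missing data in SAP | Zero is | Rule in protocol 8.4.1 | Companion analysis not zero-filled |
|---|---|---|---|---|
| BM, SBM, CSBM rate | 0 | worst value | 0, called worst case | not relevant |
| Abdominal pain, discomfort frequency | 0 | best value | none stated | severity score |
| Defecation pain frequency | 0 | best value | BM method | severity score |
| Fecal incontinence, large stools | 0 | best value | BM method | none |
| Rescue use | 0 | best value | none stated | none |

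**Missed days.** Let a patient have symptoms on B days a week with no true change, and miss m_t days a week on treatment and m_b at baseline. The spurious change is −B × (m_t − m_b)/7. With B = 5 (assumed) and m_b = 0, one missed day gives −5/7 = −0.71 days a week and two give −10/7 = −1.43. If m_t = m_b the change is 0. Protocol 4.2.1 requires at least 5 of 7 End-of-Day entries in each baseline week, so m_b is at most 2, whereas whole weeks can be zero-filled on treatment.

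**Withdrawal, one patient.** Leaving after Week 1 with 6 pain days a week (assumed) and no true change gives (6 + 0 + 0 + 0)/4 = 1.5, scored as a 4.5-day improvement. With 2 incontinence episodes a week the mean is 0.5, an improvement of 1.5.

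**Withdrawal, between arms.** Bias = weekly rate × share of weeks missing × dropout gap. The share is 3/4 if all leave after Week 1, and (3 + 2 + 1)/12 = 0.5 if departures are spread evenly over the ends of Weeks 1 to 3. Assumed rates are 5.5 pain days a week and 1 event a week. The first two gaps below come from protocol 2.1.5 (adverse-reaction discontinuations, 12-week adult trials); the other two are assumptions.

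| Dropout, active vs placebo | Pain days/week | 1 event/week |
|---|---|---|
| IBS-C 2.5% vs 0.4% | 5.5 × (0.5 to 0.75) × 0.021 = 0.058 to 0.087 | 0.011 to 0.016 |
| CIC 4.0% vs 2.0% | 5.5 × (0.5 to 0.75) × 0.020 = 0.055 to 0.083 | 0.010 to 0.015 |
| 15% vs 10% | 0.14 to 0.21 | 0.025 to 0.038 |
| 20% vs 10% | 0.28 to 0.41 | 0.05 to 0.075 |

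With equal 10% dropout there is no between-arm bias, but each arm's improvement is overstated by 0.10 × (0.5 to 0.75) = 5% to 7.5% of the weekly rate.

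**False positives.** These come from simulated trials with no true effect: 1,000 to 3,000 per scenario, 14 baseline and 28 treatment days, and 10% missed End-of-Day entries in both arms. Pain days were beta-binomial and events gamma-Poisson. Sizes were 90 vs 30 (combined Group B doses against its placebo) and 150 vs 60 (overall). The 4-week mean was tested by baseline-adjusted ANCOVA. A random-intercept model with the SAP's terms agreed (pain days at 150 vs 60: 20.0% to 31.3% by one, 21.2% to 30.1% by the other). Rescue use was tested by Mann-Whitney.

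| Dropout | Pain days, 90 vs 30 | Pain days, 150 vs 60 | 1 event/week |
|---|---|---|---|
| Equal | 4% to 6% | 4% to 6% | 4% to 6% |
| Protocol 2.1.5 gaps | near 5% | near 5% | near 5% |
| 15% vs 10% | 5% to 7% | 8% to 12% | not reported |
| 20% vs 10% | 12% to 17% | 20% to 32% | 5.5% to 11% |

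**The case against.** The case for leaving the rule alone has weight.

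- *No large gap is documented.* The two gaps in protocol 2.1.5 have little effect, and they come from 12 weeks of treatment against 4 here. This stands. But they count adverse-reaction discontinuations only, so they do not bound all-cause dropout.
- *The largest figures belong to outcomes with a safeguard.* For abdominal pain and discomfort the SAP's analysis of interest is the severity contrast "for the estimated overall average change from baseline in abdominal pain and abdominal discomfort scores across the 4-week treatment period", and for defecation pain it is the contrast "for the estimated overall average change from baseline in defecation pain and defecation pain scores across the 4-week treatment period"; neither score is zero-filled. This stands for those symptoms and does not help fecal incontinence, large stools or rescue use.
- *No error rate is claimed.* Alpha of 0.05 is set for the primary endpoint only, and the trial is exploratory without multiplicity adjustment. So 5% is only a yardstick here. The bias in the estimates remains.
- *Some missing values are true zeros.* Large stools and rescue use are logged as they occur, so no record on a completed diary day is a genuine zero. The fault lies in days without a diary and weeks after withdrawal.
- *Other outputs would reveal it.* The per-protocol repeat applies "If a diary compliance is < 70% or treatment compliance is < 80% then the subject is excluded from the PP Population", but it uses the same zero rule. The denominator for diary compliance is also undefined, so early withdrawals may or may not drop out. Disposition by arm (SAP 5.1.1) and the diary listings would expose unequal dropout without correcting for it.

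A reader might infer from protocol 8.6 that poor diary reporting automatically ends participation and so creates zero weeks. The documents do not support that. Protocol 5.2.8 calls for discussion with the medical monitor, and 6.7 makes discontinuation discretionary. Those passages need reconciling.

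**Conclusion.** The rule is wrong as written for these outcomes and should be changed. That conclusion rests on the text and needs no assumption about dropout. The size does: it is near nothing between arms at the adult gaps, modest at a 5-point gap, and material for pain days at a 10-point gap. The symptom rates and the last two gaps are assumptions.

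Two stronger conclusions are tempting. One is that the rule favours plecanatide. The documents do not show which arm will have more missing diary data, so the direction is unknown. The other is that double-digit false-positive rates are to be expected. They arise only under a dropout imbalance found nowhere in the plan. The primary SBM endpoint, where zero is the unfavourable value, is outside this point.

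**What to change.** Amend SAP 3.3.4 and the matching sentence in SAP 3.3.7, and list the change in SAP section 7.

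1. Stop imputing zero for these outcomes. Leave a week missing if it has fewer than a prespecified number of completed End-of-Day entries, for example 4; an eligible baseline week has at least 5.
2. For abdominal pain, discomfort, defecation pain and fecal incontinence, use 7 × the mean per observed day. Define an observed day as one with a completed End-of-Day entry, and count an item not asked because there was no BM as zero.
3. For large stools and rescue tablets, count every recorded event in qualifying weeks without scaling, and state that missed days within those weeks still count as zero.
4. Derive baseline the same way. Run the planned mixed model and Mann-Whitney test on observed weeks.
5. Keep zero-filling as one sensitivity analysis, and add one with an unfavourable value, for example the patient's baseline rate in missing weeks. Report missing diary data by arm.

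In the same simulations at 20% versus 10% dropout, the derivation in steps 1 to 4 gave false-positive rates of 3% to 5.5% for end-of-day symptoms, 4% to 7% for large stools and 3% to 6% for rescue use.

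The cost is a derivation change before unblinding, with no new data. Protocol section 8 lets the SAP supersede it on analyses, and the primary analysis is untouched. The downside is that the mixed model then relies on data missing at random, and the Mann-Whitney test on missingness unrelated to outcome. Events in weeks below the minimum also leave the main analysis.

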3.3.5. Imputation of Incomplete Dates

An incomplete date is any date for which either the day, month or year is unknown, but all three fields are not unknown. An incomplete date occurs when the exact date an event occurred or ended cannot be obtained from a subject. For many of the analyses, a complete date is necessary in order to determine if the event should be included in the analysis (i.e., if the event is treatment-emergent). In such cases, incomplete dates will be imputed but the collected date will be displayed on the listings.

For purposes of imputation, all events with an incomplete end date are assumed to have ended on or before the day the form was completed. In an effort to minimize bias, the project statistician will impute dates in a systematic, but reasonable manner, as described below.

Adverse Events

If the day portion of the start of the event is missing, then the start date will be set to the date of Day 1. If the day and month portion of the start of the event are missing, then these will be imputed as the day and month of Day 1. If the entire date is missing and the end date is unknown or on or after the treatment start date, then the date will be set to the treatment start date. If the month portion of the start of the event is missing and day and year are known, and day is on or after the day of the treatment start date, then month will be imputed as the month from the treatment start date. If month is missing, and day and year are known, and the day portion of the event is before the day of the treatment start date, then month will be imputed as the month after the treatment start date. If this produces an event with the end date before the start date, then the month will be imputed as the treatment start date month. If the year is missing and the day and month of the start of the event are before the day and month of enrollment, then the next year will be used (e.g. Date of enrollment = 13DEC2019, incomplete date = 03JANXXXX -> 03JAN2020). For nonexistent dates occurring at the end of a month created by this imputation method, the first date of the next month will be used (e.g. Day 1 = 31JAN2017, incomplete date = XXFEB2017 -> imputed date = 01MAR2017).

Concomitant medications

Since determining the concomitant status of medications relies primarily on the end date of the medication and study drug, only end dates will be imputed. If the day portion of the end of the medication date is missing, the day portion will be imputed as the end of the month in which it occurred. If the day and month portion of the end of the medication are missing, and the year is the same as or after the study drug treatment end date, the end of medication will be imputed as the study drug treatment end date. If the day and month portion of the end of the medication are missing, and the year is before the study drug treatment end date, the day and month portion will be imputed as 31st of December. If the entire end date of the medication is missing (and not Ongoing), then the end date of the medication will be imputed as the study drug treatment end date. If day and year of the end of the medication are recorded and month is missing, month will be imputed as the month of the study drug end date (e.g. treatment end date = 15FEB2020, incomplete date =01XXX2020 ->01FEB2020). If the day and month of the medication are recorded and the year is missing, the year will be imputed as the year of the end date of medication.

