7.4 RECORDING ADVERSE EVENTS

Adverse event assessment and reporting will extend from signing of ICF until completion of the final visit (End of the Post-Treatment Period). Adverse events occurring from the time of ICF signing up to the intake of the first dose of study medication will be classified as pre-existing conditions for this study and therefore will be recorded in the Medical History page of the eCRF. If, however, an event is considered a serious adverse event (as defined below) and occurs after the signing of informed consent but before randomization (i.e., during screening), this will be collected and reported as non-treatment-emergent Serious Adverse Events and will be recorded in the Adverse Event page of the eCRF. Events that occur from time of first dose of study drug until completion of the final study visit will be considered Treatment-Emergent Adverse Events and will be recorded on the AE page of the eCRF. Adverse events occurring after the end of the study should be reported to the Sponsor by the Investigator only if the event meets at least one seriousness criterion and the Investigator considers the causal relationship to the study drug as 'reasonably possible'.

All AE reports should contain a brief description of the event, date of onset, date of resolution, intensity, treatment required, relationship to study drug, action taken with the study drug, outcome, and whether the event is classified as serious.

All AEs experienced by patients who are randomized to treatment, regardless of the relationship to study drug, will be recorded in the eCRF. For patients who are screen failures, only SAEs (if any) will be reported on the AE page of the eCRF.

**See Section 7.6 on requirements and expectations for follow up of Adverse Events.*

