5.3.1. Adverse Events

Adverse events will be mapped to a Medical Dictionary for Regulatory Activities (MedDRA) version 23.0 preferred term and system organ classification. If a subject experiences multiple events that map to a single preferred term, the greatest severity grade (mild, moderate, or severe), and strongest investigator assessment of relation (reasonable possibility, no reasonable possibility) to study medication will be assigned to the preferred term for the appropriate summaries. Should an event have a missing severity or relationship, it will be classified as having the highest severity and/or strongest relationship to study medication. Overall summary of TEAEs will be provided. The occurrence of treatment-emergent adverse events (TEAEs) will be summarized by treatment group using preferred terms, system organ classifications, and severity. Separate summaries of treatment-emergent serious adverse events (SAEs), TEAEs related to study drug, severe TEAEs, and TEAEs leading to the discontinuation of study will be generated using system organ class and preferred terms. All adverse events reported will be listed for individual subjects showing both verbatim and preferred terms. All adverse events that occurred prior to the initiation of study treatment will be excluded from the tables but will be included in the listings.

Missing onset dates will be imputed as previously outlined in [Section 3.3.5](#) as required to determine treatment-emergent events.

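### SAP 3.3.5 gives two incompatible rules for an adverse event whose start day is missing, and neither respects the event's recorded end date

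*Combined protocol and SAP*

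**What the plan says.** SAP 3.3.5 (Adverse Events) opens with the case where the "day portion of the start of the event is missing, then the start date will be set to the date of Day 1". The sentence has no condition on the recorded month, year or end date. The next sentence works differently and, with Day 1 as its source, fills only what is absent: "If the day and month portion of the start of the event are missing, then these will be imputed as the day and month of" that reference day. Later the section adds "For nonexistent dates occurring at the end of a month created by this imputation method, the first date of the next month will be used", illustrated with Day 1 on 31JAN2017: "incomplete date = XXFEB2017 -> imputed date = 01MAR2017".

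End dates enter this list of rules twice. The rule for a wholly missing start date is conditioned on the end date. The rule for a missing month is followed by a repair for an end that precedes the start, and that repair changes only the month. The day-missing rule has neither.

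SAP 3.3.7 counts an event that started on Day 1 without an onset time as treatment-emergent. SAP 5.3.1 says "All adverse events that occurred prior to the initiation of study treatment will be excluded from the tables", though they stay in the listings. Protocol 7.4 sends non-serious events before the first dose to the Medical History page, but serious events during screening go on the AE page and are "collected and reported as non-treatment-emergent Serious Adverse Events".

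In the medication part of SAP 3.3.5, when day and month of the end date are known and the year is not, "the year will be imputed as the year of the end date of medication".

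**The concern.** The imputed start date serves mainly to decide whether an event is treatment-emergent. A rule that ignores a known month can overturn what was recorded: a start in the month before Day 1 shows that the event began before dosing, yet the sentence dates it to Day 1. The example follows a different rule, so the SAP does not define one answer. SAP 5 requires verification by independent programming, and two programmers could both follow 3.3.5 and disagree on the same event.

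What is at stake is the treatment-emergent AE and SAE tables. A screening SAE with an unknown start day could enter the treatment-emergent SAE table although protocol 7.4 says it is not treatment-emergent. Safety is part of the primary objective. No efficacy result depends on this.

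**Working it through.** **Inputs.** The day-missing sentence, the nonexistent-date rule and the example come from SAP 3.3.5. Day 1 is the first day of study drug (SAP 3.3.7). An event is taken as treatment-emergent if its imputed start is on or after Day 1. Screening lasts up to 28 days (protocol 5.2.1).

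**The two readings**

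- Sentence: imputed start = Day 1.
- Example: imputed start = recorded year and month with Day 1's day number; if that date does not exist, the first of the next month.

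**Step 1: reproduce the SAP's example.** Day 1 = 31JAN2017, start XXFEB2017. The sentence gives 31JAN2017, which is not the SAP's answer. The example's method gives 31FEB2017, which does not exist, hence 01MAR2017, which is. Neither result lies in the recorded month.

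**Step 2: treatment-emergent status by recorded month,** over all 1,461 possible Day 1 dates from 2017 to 2020:

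| Recorded month relative to Day 1's | Treatment-emergent, sentence | Treatment-emergent, example's method | Recorded month altered, example's method |
|---|---|---|---|
| One before | 1461/1461 | 0/1461 | 27/1461 |
| Same | 1461/1461 | 1461/1461 | 0/1461 |
| One after | 1461/1461 | 1461/1461 | 27/1461 |

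For the month before, the 27 are Day 1 dates of 29 to 31 March set against February (3 + 3 + 3 + 2 = 11) and the 31st of May, July, October and December in four years (16). The start then moves to the first of the Day 1 month, still before Day 1, so status is unaffected. The sentence alters the month in 1461/1461 cases in both the first and the last row.

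For instance, with Day 1 = 10FEB2020 and start XXJAN2020, the sentence gives 10FEB2020 (treatment-emergent) and the example's method gives 10JAN2020 (not).

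**Step 3: end dates** (illustrative dates, Day 1 = 20JAN2020).

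- Start XXJAN2020, end 12JAN2020. Both readings give 20JAN2020: eight days after the event ended, and treatment-emergent. Borrowing the month-missing repair would not help, because the month is already Day 1's.
- Start XXFEB2020, end 05FEB2020. The example's method gives 20FEB2020, 15 days after the event ended.

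**Step 4: calendar exposure.** Assume Day 1 is spread evenly over 2017 to 2020 and dates evenly over 28 screening days. Every month has at least 28 days, so at lag j exactly j Day 1 dates in each of 48 months look back into an earlier month. The share is 48 × (1 + … + 28) / (1461 × 28) = 48 × 406 / 40,908 = 19,488 / 40,908 = 47.6%. This is a share of dates. The documents give no number of events with partial dates.

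**Step 5: the replacement rule** (same month: Day 1; earlier: last day of that month; later: first day of that month).

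- XXFEB2017 with Day 1 31JAN2017 becomes 01FEB2017, treatment-emergent.
- XXDEC2016 with the same Day 1 becomes 31DEC2016, not treatment-emergent.
- XXJAN2020 with Day 1 10FEB2020 becomes 31JAN2020, not treatment-emergent.

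Over the same 1,461 dates, earlier-month events called treatment-emergent: 0. Recorded months altered: 0. Capping the start at the recorded end settles both cases in Step 3.

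**Step 6: medication year.** The missing year is part of the end date from which it is to be taken, so the rule returns nothing. Using the year of the study drug end date can go wrong: with treatment ending 06FEB2020 (Day 1 on 10JAN2020 for 28 days), an end of 15DECXXXX becomes 15DEC2020, ten months after treatment, and a prior drug is classed as concomitant. Taking the latest year that puts the end on or before form completion (say, in February 2020) gives 15DEC2019, before Day 1.

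**The case against.** The strongest defence is that the intended rule can be recovered. The example, and the sentence on day and month both missing, fill only the absent parts. On that reading no event from an earlier month becomes treatment-emergent. SAP 3.3.5 and 5.3.1 also confine imputation to cases where inclusion or treatment-emergent status needs it, and a recorded month before Day 1 already settles status. Exposure is slight: non-serious pre-dose events go to Medical History, protocol 7.4 asks for an onset date on every AE report, and protocol 7.5 requires SAE reports within 24 hours with a start date. No listed AE table is organised by onset time, and listings show the collected date, so a merely shifted onset does little harm. For medications, protocol 3.3 asks for month and year at minimum, so missing years should be rare.

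All of this stands as a limit on how often the rule matters. It does not choose between the readings. The as-needed wording could be stretched to events that ended before Day 1, but the SAP does not say so, and it states an end-date condition for the wholly missing date while omitting one here.

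Three stronger inferences are not supported:

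- A reader might take the worked example as a pre-treatment event turned treatment-emergent. February follows Day 1 on 31 January, so that event is treatment-emergent on any date; the example shows a contradiction and a wrong month, not a wrong status.
- A reader might note that 01MAR2017 is study Day 30, beyond the planned last dose on Day 28, and infer that the event drops out. The definition in SAP 3.3.7 has no end-of-treatment cut-off, and protocol 7.4 counts events through the final visit.
- A reader might infer that about half of pre-dose events would be misclassified. The 47.6% is a share of calendar dates, holds only under the sentence's reading, and applies to very few events.

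**Conclusion.** SAP 3.3.5 is internally contradictory for a start date with only the day missing. For an event recorded in a month before Day 1, the sentence always yields treatment-emergent and the example's method never does. The example's method can instead put the start outside the recorded month or after the event's own end. Under either reading, an event in the Day 1 month that ended before Day 1 is counted as treatment-emergent. The medication-year rule cannot be run as written.

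The reach is small: mainly screening SAEs, or pre-dose events entered on the AE page, with a partial start date. The count cannot be estimated from the documents. The conclusion rests on applying the day-missing rule as written, without an unstated end-date condition. Counting a doubtful onset in the Day 1 month as treatment-emergent is a reasonable conservative choice; it stops being reasonable once the recorded month or end date rules that onset out. A single wrong entry in the treatment-emergent SAE table would be visible in a trial with about 30 patients per group, so the text merits repair before unblinding.

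**What to change.** Replace the day-missing rule in SAP 3.3.5. When only the day is missing, keep the recorded month and year:

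- same month and year as Day 1: use Day 1;
- earlier month: use the last day of that month (not treatment-emergent by onset; worsening after dosing stays covered by the SAP 3.3.7 definition);
- later month: use the first day of that month.

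For every AE rule, state that an imputed start is never later than the event's recorded end date. Delete the XXFEB2017 example.

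For a medication end date with a missing year, use the latest year that places it on or before the day the form was completed. This is the assumption that SAP 3.3.5 already makes for incomplete end dates. Do not simply substitute the year of the study drug end date.

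The cost is a few lines of SAP text and code, with no effect on data collection. The one downside is a slightly less conservative treatment-emergent count for events whose recorded month or end date precedes Day 1.
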